11.2 Toxicity Management

Routine supportive care is recommended. Routine prophylactic use of G-CSF is not permitted. Please refer to Table 11 for toxicity specific modifications.

Table 11: Criteria for interruption and re-initiation of buparlisib treatment

Worst toxicity (CTCAE 4.03 Grade)**	Dose Modifications for Buparlisib
HEMATOLOGICAL	
Neutropenia (ANC)	
Grade 1 (ANC < LLN - $1.5 \times 10^9/L$) Grade 2 (ANC < $1.5 - 1.0 \times 10^9/L$)	Maintain dose level
Grade 3 (ANC < $1.0 - 0.5 \times 10^9/L$) Grade 4 (ANC < $0.5 \times 10^9/L$)	Omit dose until resolved to \leq Grade 1, then: If resolved in ≤ 7 days, then maintain dose level If resolved in > 7 days, then $\downarrow 1$ dose level
Febrile neutropenia (ANC < $1.0 \times 10^9/L$, with a single temperature of ≥ 38.3 °C or a sustained temperature of ≥ 38 °C for more than one hour)	Omit dose until resolved, then $\downarrow 1$ dose level
Thrombocytopenia	
Grade 1 (PLT < LLN - $75 \times 10^9/L$) Grade 2 (PLT < $75 - 50 \times 10^9/L$)	Maintain dose level
Grade 3 (PLT < $50-25 \times 10^9/L$)	Omit dose until resolved to \leq Grade 1, then: If resolved in ≤ 7 days, then maintain dose level If resolved in > 7 days, then $\downarrow 1$ dose level
Grade 4 (PLT < $25 \times 10^9/L$)	Omit dose until resolved to \leq Grade 1, then $\downarrow 1$ dose level
RENAL	
Serum creatinine	
Grade 1 (< 2 x ULN)	Maintain dose level
Grade 2 (2 – 3 x ULN)	Omit dose until resolved to \leq grade 1, then: If resolved in ≤ 7 days, then maintain dose level If resolved in > 7 days, then $\downarrow 1$ dose level
Grade 3 (> 3.0 – 6.0 x ULN)	Permanently discontinue patient from buparlisib
Grade 4 (> 6.0 x ULN)	Permanently discontinue patient from buparlisib
HEPATIC	
Bilirubin (*for patients with Gilbert Syndrome these dose modifications apply to changes in direct bilirubin only) will be fractionated if elevated	
Grade 1 (> ULN - $1.5 \times ULN$)	Maintain dose level with LFTs* monitored as per protocol
Grade 2 (> $1.5 - 3.0 \times ULN$) with ALT or AST $\leq 3.0 \times ULN$	Omit dose until resolved to \leq Grade 1, then: If resolved in ≤ 7 days, then maintain dose level If resolved in > 7 days, then $\downarrow 1$ dose level
Grade 3 (> $3.0 - 10.0 \times ULN$) with ALT or AST $\leq 3.0 \times ULN$	Omit dose until resolved to \leq Grade 1, then: If resolved in ≤ 7 days, $\downarrow 1$ dose level If resolved in > 7 days discontinue patient from buparlisib
Grade 4 (> $10.0 \times ULN$)	Permanently discontinue patient from buparlisib

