AST or ALT	
Grade 1 (> ULN – $3.0 \times ULN$)	Maintain dose level with LFTs* monitored per protocol

MEMORIAL SLOAN-KETTERING CANCER CENTER
IRB PROTOCOL

IRB#: 14-177 A(5)

Grade 2 (> 3.0 - 5.0 x ULN) without total bilirubin elevation to > 2.0 x ULN	Can continue treatment at ↓ 1 dose level
Grade 3 (> 5.0 - 20.0 x ULN) without total bilirubin elevation to > 2.0 x ULN	Omit dose until resolved to ≤ Grade 1, then ↓ 1 dose level** If no recovery in ≤28 days, discontinue buparlisib permanently
Grade 4 (> 20.0 x ULN) without bilirubin elevation to > 2.0 x ULN	Discontinue buparlisib permanently
AST or ALT and concurrent Bilirubin	
AST or ALT > 3.0 x ULN and total bilirubin > 2.0 x ULN	Permanently discontinue buparlisib***

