
*(LFTs include albumin, ALT, AST, total bilirubin (fractionated if total bilirubin > 2.0 x ULN), alkaline phosphatase (fractionated if alkaline phosphatase is grade 2 or higher) and GGT)
 
**In case of recurring Grade 3 or higher toxicity after re-challenge, patient should be permanently discontinued
 
***All patients with ALT or AST>3.0x ULN and total bilirubin >2.0x ULN in the absence of cholestasis must immediately be withdrawn from buparlisib and every attempt should be made to carry out the liver event follow-up assessments as described below in section 11.11.1.2: Management of Hepatotoxicity (ALT and/or AST> 3.0x ULN and total bilirubin >2.0x ULN) in patients receiving buparlisib and Viral Serology and other tests for hepatotoxicity follow-up.
 
Hepatic toxicity monitoring (*for patients with Gilbert Syndrome: total and direct bilirubin must be monitored, intensified monitoring applies to changes in direct bilirubin only; the monitoring includes the following LFTs: albumin, ALT, AST, total bilirubin (fractionated if total bilirubin > 2.0 x ULN), alkaline phosphatase (fractionated if alkaline phosphatase is grade 2 or higher) and GGT):
 
Cycle 1 and 2: every other week (if visit schedule allows a more frequent monitoring this should be considered) or more frequently if clinically indicated especially for patients with borderline acceptable AST/ALT, or bilirubin* values
 
Cycle 3 and onward: monthly or more frequently if clinically indicated
 
In case of any occurrence of ALT/AST, or bilirubin* increase ≥ grade 2 the liver function tests must be monitored weekly or more frequently if clinically indicated until resolved to ≤ grade 1
 
In case of any occurrence of ALT/AST, or bilirubin* increase ≥ grade 3 the liver function tests must be monitored weekly or more frequently if clinically indicated until resolved to ≤ grade 1; hereafter the monitoring should be continued every other week or more frequently if clinically indicated until the end of treatment with study medication
 
Patients who discontinued study treatment should be monitored weekly, including LFTs* or more frequently if clinically indicated until resolved to ≤ grade 1 or stabilization (no CTCAE grade change over 4 weeks).
	
ENDOCRINE/METABOLIC	
Fasting Plasma Glucose (FPG)	

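### Table 11: for patients with one raised transaminase, the bilirubin Grade 2 and 3 rows overlap the combined liver row, and the cholestasis qualifier leaves the re-challenge question open

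*Combined protocol and SAP*

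**What the plan says.** All of this is in the combined protocol and SAP, mainly the hepatic part of Table 11 (section 11.2).

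- Bilirubin Grade 2 row: "Grade 2 (> $1.5 - 3.0 \times ULN$) with ALT or AST $\leq 3.0 \times ULN". Drug is held until Grade 1 or better, then "If resolved in ≤ 7 days, then maintain dose level If resolved in > 7 days, then $\downarrow 1$ dose level".
- Bilirubin Grade 3 row: "Grade 3 (> $3.0 - 10.0 \times ULN$) with ALT or AST $\leq 3.0 \times ULN". Drug is held and restarted one level lower if the event resolves in 7 days or less; otherwise "If resolved in > 7 days discontinue patient from buparlisib".
- Bilirubin Grade 4 row: "Grade 4 (> $10.0 \times ULN". Permanent stop, with no enzyme condition.
- Combined row: "AST or ALT > 3.0 x ULN and total bilirubin > 2.0 x ULN". The action is "Permanently discontinue buparlisib", with a pointer to footnote ***. The row carries no CTCAE grade and does not mention cholestasis.
- Footnote ***: "All patients with ALT or AST>3.0x ULN and total bilirubin >2.0x ULN in the absence of cholestasis must immediately be withdrawn from buparlisib". Section 11.11.1.2 repeats this instruction with the same qualifier and describes cholestasis through raised alkaline phosphatase.
- Section 9.1 bases dose changes on the worst toxicity as graded by CTCAE.

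No sentence says which row governs when a bilirubin row and the combined row are both met.

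**The concern.** The table appears meant to sort each liver result into one action. The AST/ALT Grade 2 to 4 rows exclude total bilirubin above 2.0 x ULN so that the combined row can take over, and the enzyme condition in the bilirubin rows looks like the matching exclusion. It does not work as one, because a single low enzyme satisfies the bilirubin rows while a single high enzyme satisfies the combined row. A patient with discordant enzymes can satisfy both.

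At stake is whether a patient with raised bilirubin and a raised transaminase may be re-challenged with study drug or must stop for good. Two investigators could follow the table correctly and act differently on the same laboratory result.

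**Working it through.** No sample-size or power figure is involved, so the check is one of logic. Let A = ALT, S = AST and B = bilirubin, each in multiples of ULN. Read literally, the rows are:

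- Bilirubin Grade 2: 1.5 < B ≤ 3.0 and min(A, S) ≤ 3.0
- Bilirubin Grade 3: 3.0 < B ≤ 10.0 and min(A, S) ≤ 3.0
- Bilirubin Grade 4: B > 10.0
- Combined: max(A, S) > 3.0 and B > 2.0

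A Grade 2 or 3 bilirubin row and the combined row hold together exactly when min(A, S) ≤ 3.0 < max(A, S) and 2.0 < B ≤ 10.0.

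| ALT | AST | Bilirubin | Rows met | Actions |
|---|---|---|---|---|
| 4.0 | 2.5 | 2.5 | Bilirubin Grade 2; combined | hold then restart; permanent stop |
| 4.0 | 2.5 | 3.5 | Bilirubin Grade 3; combined | hold, restart if resolved in ≤ 7 days; permanent stop |
| 4.0 | 2.5 | 10.5 | Bilirubin Grade 4; combined | both permanent stop |
| 4.0 | 4.0 | 2.5 | Combined only | permanent stop |
| 2.0 | 2.0 | 2.5 | Bilirubin Grade 2, not combined | hold then restart |

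A grid in steps of 0.25 (enzymes 0.5 to 25, bilirubin 0.5 to 15) confirms the region. It has 11 enzyme values at or below 3.0, 88 above, and 32 bilirubin values above 2.0 and up to 10.0. The overlap is 2 × 11 × 88 × 32 = 61,952 points, all with exactly one enzyme above 3.0. If the bilirubin rows are read as requiring both enzymes at or below 3.0, the overlap is 0. The counts describe the grid, not patients.

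**How far the actions differ.** Both rows interrupt drug immediately. Under bilirubin Grade 2, restart is possible whether resolution takes 7 days or longer (subject to the 28-day limit on holds in sections 9.1 and 9.2), against a permanent stop. Under bilirubin Grade 3, the conflict exists only if the event resolves in 7 days or less; after that, both rows discontinue.

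**What the footnote settles.** Without cholestasis, footnote *** and section 11.11.1.2 require withdrawal of everyone who meets the combined criterion. With cholestasis, the combined row still says stop, the footnote and section 11.11.1.2 give no withdrawal instruction, and the bilirubin row says hold with possible restart.

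**What the worst-toxicity rule settles.** At ALT 4.0 and bilirubin 2.5, both values lie in Grade 2 bands of Table 11 (>3.0–5.0 and >1.5–3.0). The combined row has no grade, so a ranking by grade cannot select or reject it.

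**Two related effects.** At ALT 4.0, AST 2.5 and bilirubin 1.8, the bilirubin Grade 2 row (hold) and the AST/ALT Grade 2 row (continue one level lower) are both met, at equal grade. In Gilbert syndrome the bilirubin rows use direct bilirubin and the combined row uses total, so the two rows rest on different measures.

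**The case against.** The best defence is that the intended reading is clear. The combination has its own block, the AST/ALT rows hand over to it explicitly, and the bilirubin qualifier is most sensibly read as neither enzyme being above 3.0 x ULN. On that reading the overlap disappears. Footnote *** then orders immediate withdrawal in mandatory terms, and section 11.11.1.2 repeats it.

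Much of this stands. For a patient without cholestasis the footnote is strong enough that most investigators would stop the drug. The rest does not close the gap. The same connective would have to mean both enzymes in the bilirubin rows and either enzyme in the combined row, which the footnote's own cross-reference restates as and/or. The footnote also adds a condition that the row lacks.

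A reader might infer more than the documents support:

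- *That the plan gives no guidance at all when both rows match.* The footnote and section 11.11.1.2 give it for non-cholestatic patients.
- *That about 2 to 6 patients are affected.* Section 11.11.1 puts single-agent Grade 3 and 4 liver events at about 10 to 30%, and 21 × 0.10 = 2.1, 21 × 0.30 = 6.3. That counts all such events regardless of cause. The section adds that they were mostly transaminase rises and that few patients had accompanying signs such as raised bilirubin. No frequency is given for discordant enzymes.
- *That the six cases consistent with Hy's law show this risk for the present regimen.* Five were on the fulvestrant combination and one on the LDE225 combination, and nothing is said about discordant enzymes.

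**Conclusion.** The inconsistency is real, but narrower than the raw overlap suggests. It covers one enzyme above 3.0 x ULN, the other at or below it, and bilirubin above 2.0 and up to 10.0 x ULN. Within that region the rows conflict on re-challenge, not on immediate interruption, and they agree when Grade 3 bilirubin takes more than 7 days to resolve. For non-cholestatic patients the footnote and section 11.11.1.2 largely decide the matter. For cholestatic patients with discordant enzymes, nothing in the plan does.

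The conclusion rests on the ordinary reading of the enzyme condition as at least one of the two. The number of patients cannot be estimated from the documents and is probably small. A reader might also infer damage to the primary endpoint. Section 12.8 defines PFS by progression or death, not by stopping drug for toxicity, so the analysis method is unaffected. This is a contradiction in operative safety instructions that should be corrected.

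**What to change.** Reconcile four places together: the bilirubin Grade 2 and 3 rows, the combined row, footnote *** and section 11.11.1.2. Either word the enzyme conditions so that no set of ALT, AST and bilirubin values meets both a hold-and-restart row and the permanent-stop row, or add a line under Table 11 saying which row governs when both match. The same pass should:

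- make the cholestasis qualifier consistent, either in all of these places or in none;
- resolve the tie between the bilirubin Grade 2 and AST/ALT rows at bilirubin above 1.5 and up to 2.0 x ULN;
- state which bilirubin measure the combined row uses in Gilbert syndrome.

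Afterwards, run the worked examples above through the revised table; any pair of differing actions that the worst-toxicity rule cannot rank by grade should be gone. Which action applies in each case is the sponsor's medical decision, and none is proposed here.

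The cost is a wording amendment, with no extra tests, visits or patients.

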- Patient has an uncontrolled intercurrent illness, including, but not limited to, ongoing or active infection, chronic liver disease, chronic renal disease, pancreatitis, chronic pulmonary disease, or psychiatric illness or social situations that would limit compliance with the study requirements
- Patient has acute viral hepatitis or a history of chronic or active HBV or HCV infection
- Patient has an active concurrent malignancy requiring active therapy.
- Patient is known to have human immunodeficiency virus (HIV) infection
- Patient has any severe psychiatric disease that would interfere with participation in the trial as determined by the study investigator
- Patient has \geq CTCAE grade 3 anxiety
- Patient has \geq CTCAE grade 2 diarrhea
- Patient has a score ≥ 12 on the PHQ-9 questionnaire
- Patient selects a response of “1, 2 or 3” to question number 9 on the PHQ-9-questionnaire regarding potential for suicidal thoughts or ideation (independent of the total score of the PHQ-9).
- Patient has a GAD-7 mood scale score ≥ 15 .
- Patient has a medically documented history of or active major depressive episode, bipolar disorder (I or II), obsessive-compulsive disorder, schizophrenia, a history of suicidal attempt or ideation, or homicidal ideation (e.g. risk of doing harm to self or others).
- Patient has active cardiac disease or cardiac dysfunction including any of the following:
 - Left ventricular ejection fraction (LVEF) $\geq 50\%$ as determined by Multiple Gated Acquisition (MUGA) scan or echocardiogram (ECHO)
 - QTc >480 msec on screening ECG (using the QTcF formula)
 - Angina pectoris that requires the use of anti-anginal medications
 - Ventricular arrhythmias except for benign premature ventricular contractions
 - Supraventricular and nodal arrhythmias requiring a pacemaker or not controlled with medication
 - Conduction abnormality requiring a pacemaker
 - Valvular disease with documented compromise in cardiac function
 - Symptomatic pericarditis
 - Myocardial infarction within the last 6 months, documented by persistent elevated cardiac enzymes or persistent regional wall motion abnormalities on assessment of left ventricular ejection fraction function
 - History of documented congestive heart failure (New York Heart Association functional classification III-IV)
 - Documented cardiomyopathy
 - Congenital long QT syndrome

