When treatment must be held pending resolution of toxicity to grade 1 or return to baseline, and the toxicity is a lab abnormality, in cases where the participant had a pre-existing laboratory abnormality at baseline, the toxicity can be considered “resolved from a hold perspective when it has resolved to within 1 grade of the baseline value.

NOTE: For the purposes of data entry, value from screening assessments should be entered in as “baseline values.” However, true “baseline values” for the purpose of dose modifications on study will be considered the last assessments or tests performed prior to initiation of study therapy.

Exception: In instances where the value within 1 grade of the baseline value would still require a hold, continue to hold until resolution of toxicity to grade 1 or return to baseline.

Participants who experience an adverse event that requires a treatment delay or dose reduction should be monitored with appropriate laboratory testing or other clinical evaluation at least weekly until resolution.

Following a dose delay which resumes mid cycle, day 1 procedures not associated with the adverse event do not need to be repeated.

No more than 4 levels of dose reduction are permitted in this study. Participants cannot be treated below dose level -4. If a participant whose buparlisib dose has been reduced by 4 dose levels requires another dose reduction, treatment on study must be stopped unless the participant has benefited from the study, in which case the investigator will contact the Principal Investigator to determine if the participant will remain in the study.

A treatment delay of up to 28 days is permitted. If the toxicity has not resolved after a 4 week delay, the participant must be removed from study treatment unless the participant has benefited from the study, in which case, the investigator may contact the Principal Investigator to determine if the participant will remain in the study.

Dose re-escalation is never permitted in this study.

MEMORIAL SLOAN-KETTERING CANCER CENTER IRB PROTOCOL

IRB#: 14-177 A(5)

Cycle length will be 4 weeks (28 days), even if treatment is held for toxicity. There is no stopping in counting cycles/days for those periods where a subject's drug is withheld. All study evaluations and treatments should continue as if study treatment is not being held.

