9.2 Treatment interruption and treatment discontinuation

If the study drug is being held due to toxicity, scheduled visits and all assessments should continue to be performed, with the exception of the dosing of the held study drug. If treatment with the study drug is withheld for ≥ 28 days, then the study drug must be permanently discontinued. Patients who permanently discontinue the study drug should have a follow up at approximately 30 days after discontinuation of all study treatment or resolution of the adverse event to \leq grade 1, whichever occurs first, that includes all study assessments appropriate to monitor the event.

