10.0 EVALUATION DURING TREATMENT/INTERVENTION

10.1 General Requirements

Table 6 describes the required procedures. All procedures may increase in frequency if clinically indicated or oriented following a toxicity/adverse event.

A complete history, vital signs (including blood pressure, pulse, respiratory rate, temperature, weight and height), physical and neurological examination (to include documentation of the patients Karnofsky performance status (Appendix 6) and NANO score as well as a serum pregnancy test for women of childbearing potential will be performed on day 1 (+/- 4 days) of each cycle.

Neuro-imaging (including contrast-enhanced MRI/CT brain and total spine) and/or CSF collection (for patients with CSF disease; through Ommaya or spinal tap; including cytology) will need to be performed on all patients on day 1 cycle 3, and each additional odd numbered cycle (+/- 4 days). Imaging will include only the side of active disease (MRI brain for patients with brain disease; MRI total spine for patients with intraspinal disease; MRI brain and total spine for patients with brain and spine disease as well as leptomeningeal disease) or sides suggested by new neurologic symptoms and signs. All MRI imaging will included MR perfusion . If MRI spectroscopy is additionally performed, we will collect the additional data.

CBC with differential, platelets, sodium, potassium, calcium, AST, ALT, alkaline phosphatase, total bilirubin, fasting plasma glucose, creatinine, will need to be performed at day 1 and day 15 of each cycle and at the end of the treatment (+/- 4 days).

Amylase and lipase need to be assessed at the end of the treatment (+/- 4 days).

Chest X-ray and 12-lead ECG need to be done every other cycle starting at day 1 of cycle 3 (+/- 4 days)

Participants need to complete the PHQ-9 and GAD7 self rating mood scale (see Appendix 6).at day 1 and day 15 of cycle 1 and 2. On each consecutive cycle only on day 1 and at the

**MEMORIAL SLOAN-KETTERING CANCER CENTER
IRB PROTOCOL**

IRB#: 14-177 A(5)

end of treatment (+/- 4 days). Questionnaires can be performed over the phone on Cycle 2 Day 15 by research staff, if the participant is not able to physically attend to clinic.

Table 6: Required Activity Calendar

Tests and procedures	Screening	On trial						
		Prior to Registration	Cycle 1		Subsequent cycles		End of treatment	30-day post drug
			Day 1	Day 15	Day 1	Day 15		
Informed consent	X							
Inclusion/exclusion criteria	X							

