	
 ● instruct patient to follow dietary guidelines according to local and/or institutional standards for management of diabetes mellitus (such as those provided by the American Diabetes Association) during the study ● consider use of oral anti-hyperglycemic therapy such as metformin ● check FPG at least weekly for 8 weeks, then continue checking at least every 2 weeks if clinically indicated 
For non-fasting plasma glucose >500 mg/dL (> 27.8 mmol/L) accompanied by signs/symptoms of hyperglycemia (for example, mental status changes, excessive thirst, polyuria), or presence of blood or urine ketones, discontinue buparlisib and following guidance for management of Grade 4 fasting plasma glucose (FPG).

CARDIAC	
Cardiac - Left Ventricular systolic dysfunction	
Asymptomatic, resting ejection fraction 40-50%; or 10-20% drop from baseline	Maintain dose level, and continue buparlisib with caution Repeat LVEF within 4 weeks or as clinically appropriate
Symptomatic, responsive to intervention, ejection fraction 20-39% or > 20% drop from baseline	
 ● Omit buparlisib until resolved* (as defined below), then ↓ 1 dose level ● LVEF measurement to be repeated, if not resolved* within 21 days, permanently discontinue patient from buparlisib treatment
Refractory or poorly controlled, ejection fraction < 20%	● Permanently discontinue patient from buparlisib
*the event is considered resolved when the patient is asymptomatic, has a resting ejection fraction ≥ 40% and ≤20% decrease from baseline.	
Cardiac – QTc prolongation	
QTcF > 500 ms (≥ Grade 3) or > 60 ms change from baseline on at least two separate ECGs	
First Occurrence:
 
 ● omit buparlisib ● Perform an analysis of serum potassium and magnesium, and if below lower limit of normal, correct with supplements to within normal limits. Concomitant medication usage must be reviewed. ● Perform a repeat ECG within one hour of the first QTcF of > 500 ms or >60ms from baseline ● If QTcF remains > 500 ms or >60ms from baseline, repeat ECG as clinically indicated, but at least once a day until the QTcF returns to < 480 ms. Seek cardiologist input. ● Once QTcF prolongation has resolved, buparlisib may be restarted at a one lower dose level 
Second Occurrence:
 
 ● Permanently discontinue patient from buparlisib
Other Cardiac Events	
Grade 1 or 2	Maintain dose level

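### Table 11, QTc row: daily ECGs can start on a rise of more than 60 ms from baseline but end on QTcF below 480 ms alone, so below a 420 ms baseline they can lapse while the trigger persists

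*Combined protocol and SAP*

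**What the plan says.** The QTc prolongation row of Table 11 (Section 11.2) is triggered by "QTcF > 500 ms (≥ Grade 3) or > 60 ms change from baseline on at least two separate ECGs". At a first occurrence the drug is omitted, potassium and magnesium are checked and corrected, concomitant medication is reviewed, and an ECG is repeated within an hour. If that ECG still shows either limb, the row says to "repeat ECG as clinically indicated, but at least once a day until the QTcF returns to < 480 ms", and asks for cardiologist input.

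Restart is a separate bullet: "Once QTcF prolongation has resolved, buparlisib may be restarted at a one lower dose level". The row does not define resolution in numbers.

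Other text that bears on the point:

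- Section 6.2 sets only an upper limit at entry: "QTc >480 msec on screening ECG (using the QTcF formula".
- Section 9.1 fixes the baseline that "for the purpose of dose modifications on study will be considered the last assessments or tests performed prior to initiation of study therapy".
- Section 9.1 also says that patients whose adverse event requires a delay or reduction "should be monitored with appropriate laboratory testing or other clinical evaluation at least weekly until resolution".
- Section 10.1 adds: "All procedures may increase in frequency if clinically indicated or oriented following a toxicity/adverse event".

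**The concern.** The row treats a rise of more than 60 ms as sufficient reason, by itself, to hold the drug and to require ECGs at a stated minimum frequency. It then lets that minimum end on a test that takes no account of the rise. A patient with a low baseline can pass the test while the reason for the hold is still present. From then on, ECG frequency rests on clinical judgment and the general follow-up rules.

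The neighbouring row for left ventricular dysfunction shows the more complete form. It also has absolute and relative triggers, and it counts the event as resolved only when the patient has no symptoms, the ejection fraction is at least 40%, and the fall from baseline is no more than 20%. Both limbs are closed there; in the QTc row one is left open.

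The matter at stake is patient safety during a hold. Section 10.2 gives an effective half-life of about 40 hours, so exposure falls over days, and those are the days in which a daily minimum is useful.

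**Working it through.** The plan states no figure for this point, so the check is on the logic of the thresholds. Let *b* be baseline QTcF and *q* the current QTcF, both in ms, with change from baseline read as an increase.

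**Inputs**

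- Daily ECGs start (Table 11): *q* > 500 or *q* − *b* > 60, after confirmation on at least two ECGs.
- Daily ECGs stop (Table 11): *q* < 480.
- Eligible baselines (Section 6.2): up to 480, with no lower limit.
- Baseline (Section 9.1): the last test before the first dose.

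**Step 1: when can the stop be met while the trigger persists?** The absolute limb cannot persist, because *q* < 480 rules out *q* > 500. The relative limb persists when

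*b* + 60 < *q* < 480.

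This range is non-empty when *b* + 60 < 480, that is *b* < 420. In whole milliseconds it runs from *b* + 61 to 479, which is 419 − *b* values, so the highest affected baseline is 418.

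**Step 2: size of the window.** Readings that trigger on the relative limb alone run from *b* + 61 to 500, which is 440 − *b* values.

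| Baseline | Relative limb alone | Values | Also below 480 | Values |
|---|---|---|---|---|
| 380 | 441–500 | 60 | 441–479 | 39 |
| 400 | 461–500 | 40 | 461–479 | 19 |
| 410 | 471–500 | 30 | 471–479 | 9 |
| 418 | 479–500 | 22 | 479 | 1 |
| 419 | 480–500 | 21 | none | 0 |

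These are counts of possible readings, not probabilities.

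**Step 3: two cases at baseline 400.**

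- *Peak 510, falling to 475.* At the peak, 510 > 500 and 510 − 400 = 110 > 60, so once confirmed both limbs are met. At 475 the stop is met (475 < 480), yet 475 − 400 = 75 > 60. The daily minimum has lapsed while the relative trigger persists.
- *465, confirmed on a second ECG.* 465 − 400 = 65 > 60, so the hold applies and the daily-ECG bullet opens. But 465 is already below 480. A value that was never at 480 or above cannot strictly return below it, so the text does not settle whether the daily minimum applies.

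**Step 4: effect of adding the relative limb to the stop.** If the stop requires *q* < 480 and *q* − *b* ≤ 60, neither trigger can be present when it is met, at any baseline. For *b* ≥ 420, *q* < 480 already gives *q* − *b* < 60, so the stop is unchanged there.

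**The case against.** The strongest reply is that the absolute stop may be deliberate and that the gap is well covered. The affected patient is off drug, and a QTcF below 480 ms is a level that Section 6.2 accepts for enrolment. Electrolytes have been checked, concomitant drugs reviewed and a cardiologist consulted. ECGs as clinically indicated continue, and Sections 9.1 and 10.3 require at least weekly follow-up for four weeks and then every four weeks until resolution or stabilization. QT prolongation is also absent from the suspected drug-related events listed in Section 11.1.

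Most of this stands, and it is why the point is minor. It does not replace the missing limb. The weekly rule in Section 9.1 names laboratory testing or other clinical evaluation, not an ECG. Section 10.1 permits more frequent procedures without requiring them. The scheduled ECG is only every other cycle from cycle 3. A deliberate absolute stop also sits poorly with a bullet that itself makes a rise above 60 ms enough to start daily ECGs.

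Two stronger readings are tempting, and neither is supported.

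- *A reader might infer that the drug could be restarted while the patient is still more than 60 ms above baseline.* Restart is a separate bullet requiring that prolongation has resolved, which most naturally means that neither trigger is still met. Nothing ties it to the 480 ms figure.
- *A reader might infer that daily ECGs never apply to a patient such as the one confirmed at 465.* The bullet's opening condition is met for that patient, and a clinician could reasonably keep repeating ECGs while it persists. The wording is ambiguous; it does not plainly switch monitoring off.

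**Conclusion.** The point holds as a minor patient-safety correction and a cheap improvement. For any eligible baseline below 420 ms (418 ms or lower if QTcF is recorded in whole milliseconds), the stated minimum of daily ECGs can lapse while the relative trigger is still met. For readings that never reach 480 ms, it is unclear whether the minimum applies.

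How many of the 21 patients this would touch is unknown, because the documents give neither a distribution of baseline QTcF nor a rate of QTc events. The conclusion concerns ECG frequency during a hold and nothing else. PFS24w and the rule of at least 12 of 21 patients progression-free are not affected.

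**What to change.** In the daily-ECG bullet of the QTc row, make the stop require both conditions: QTcF below 480 ms, and no more than 60 ms above the Section 9.1 baseline. This also settles the ambiguous case, since the daily minimum then continues until the rise itself has come down.

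Leave the restart bullet unchanged. No defect in it is shown, and carrying the 480 ms limit into it would have side effects. On the natural reading of resolved, a patient with baseline 450 who peaks at 505 and recovers to 490 (490 − 450 = 40) may restart now but would be barred. A patient with the highest eligible baseline, 480, could return exactly to baseline and still be barred. Either could then run into the Section 9.2 rule: "If treatment with the study drug is withheld for ≥ 28 days, then the study drug must be permanently discontinued".

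The cost is one table cell and a few extra ECGs for some held patients with baselines below 420 ms, using a procedure the row already requires. The ECG stop is unchanged at baselines of 420 ms or more, and the hold and restart rules are unchanged for everyone.
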